However, currently, the routine use of prophylactic drains after colorectal surgery is still widespread (15). As part of our last EuroSurg study, IMAGINE (16), centres filled out a survey regarding their adherence to ERAS guidelines. Preliminary data has shown that 35% of participating centres routinely leave drains after colorectal surgery for most of their patients.

Reasons to justify drainage after colorectal surgery include: prevention of complicated intra-abdominal collections; early detection of haemorrhage, anastomotic leakage, or other complications, and reduction of the incidence of anastomotic leak and pelvic sepsis (17,18). On the other hand, the routine placement of prophylactic drains is also associated with adverse events. Drains have been shown to be associated with an increased production of serous fluid, which could lead to wound infections, promote adhesions and could even result in a higher risk of anastomotic leak (19,20). In addition, they could cause irritation and offer an inward track for contamination.

It is common opinion that early detection of intra-abdominal collections might prevent additional surgical or percutaneous procedures necessary during the postoperative period (21). However, there is no consensus on which type of drain should be used and for how long it should be left in situ.

The aim of this international multi-centre cohort study is to define the incidence of drain placement after colorectal surgery and to describe drain management practices.

Methods

1. Definition for intra-abdominal collections

Postoperative collection altering the normal postoperative course management and requiring antibiotics or radiological/endoscopic/surgical intervention.

2. Summary

“Mini-teams” of up to three collaborators (medical students and/or doctors) per data collection period will prospectively collect data over a continuous 14-day period at each participating centre. This will be on consecutive patients undergoing elective or emergency colorectal surgery, with follow-up to 30 postoperative days. All mini-teams should be supervised by one surgical consultant of reference per centre. Each participating centre will be required to fill out a survey regarding their local drain management practices.

3. Study Aims

- **Primary Aim:** To audit compliance to Enhanced Recovery After Surgery (ERAS) guidelines on avoiding routine placement of prophylactic drains in colorectal surgery.
- **Secondary Aims:**

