 - To assess whether placement of a postoperative drain is associated with earlier detection of collections and anastomotic leak.
 - To examine when drains can be safely removed.
 - To explore the clinical decision-making process for drain placement after colorectal surgery.
 - To characterise the incidence of complicated postoperative collections and their clinical management in colorectal surgery in an international cohort.

4. Project Timeline

Data collection will take place between 3rd February 2020 and 26th April 2020 during the following four predefined 14-day data collection periods.

- **Period 1:** 08:00 AM 3 Feb 2020 to 08:00 AM 17 Feb 2020 (+ 30 Day Follow-up)
- **Period 2:** 08:00 AM 24 Feb 2020 to 08:00 AM 09 Mar 2020 (+ 30 Day Follow-up)
- **Period 3:** 08:00 AM 16 Mar 2020 to 08:00 AM 30 Mar 2020 (+ 30 Day Follow-up)
- **Period 4:** 08:00 AM 13 Apr 2020 to 08:00 AM 27 Apr 2020 (+ 30 Day Follow-up)

An extra period may be opened at the discretion of the steering committee to allow for the participation of centres that encountered difficulties in obtaining the necessary ethical approvals:

- **Period 5:** 08:00 AM 27 Apr 2020 to 08:00 AM 11 May 2020 (+ 30 Day Follow-up)

At each hospital, one mini-team per period will collect data on eligible patients admitted over a 14-day period. Data on 30-day outcomes after the day of surgery will also be collected. The deadline for uploading collected data onto REDCap is 30th June 2020.

Patients should be included if their operation started (defined as 'knife-to-skin' time) within the time period during the data collection periods as specified above.

One mini-team of up to three collaborators can take part in each 14-day period. Multiple mini-teams can participate at each centre, but no more than one team per period at the same centre. To be listed as PubMed-citable collaborators, centres are required to participate in at least one data collection period.

5. Centres

- COMPASS is open to any hospital in the member countries of the European Society of Coloproctology (ESCP), the Royal Australasian College of Surgeons (RACS) and South African centres, which routinely perform elective or emergency colorectal surgery. Participation of centres from other countries will be considered on a case-by-case basis.

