Criteria for centre inclusion within COMPASS:

- ▲ ● Successful completion of **at least one data collection period** at the centre (with a minimum of one eligible patient per period included). ▲
- Obtain all appropriate **local approvals** for conduct of the COMPASS audit.
- Individual data collection periods will only be included when:
 - I. >95% data completeness has been achieved.
 - II. Validation targets have been achieved (if performed).
 - III. All data for the period has been uploaded within the specified deadlines.

Please note if these criteria are not met, then the contributing mini-team and/or the centre may be removed from the dataset and authorship list (get in contact asap with potential issues arise so we can support your centre to be included). See Appendix D for advice to help ensure successful inclusion of your centre in the COMPASS audit.

16. Patient and Public Involvement

To better understand the role of drains in colorectal surgery and their impact on the post-operative period, we asked the opinion of patients, aiming to clarify what matters to them most in the post-operative period. Patients were invited to fill out an anonymous survey through social media. The main questions concerned their experience with drains in the post-operative period, with an emphasis on to which extent, in their opinion, the drain(s) facilitated / slowed down their recovery. Patients were also asked whether anyone discussed with them the possibility of placing a drain during surgery and to give their opinion regarding which are the most important outcomes a study focussed on surgical drains should explore.

Patients were concerned about possible post-operative complications and felt that their doctors placed a drain to prevent them. However, at the same time, they feared the drain might have slowed down their recovery as it caused severe pain and it significantly reduced their mobility and, therefore, independence. In light of their replies, we structured our study to capture the drain management practices of an international cohort of colorectal surgeons. We used the patients' insight to formulate a centre survey and case report form that will help us explore whether most surgeons adhere with the Enhanced Recovery After Surgery (ERAS) guidelines and, if not, understand their reasons for not being compliant.

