Intraoperative complications	None / Vascular injury / Bowel injury (e.g. duodenum) / Injury to other organs or structures (e.g. ureter)
Abdominal drain(s) inserted at time of surgery	Yes / No
Reason for drain identified	
Not identified Excessive intraoperative blood loss (or concern regarding this). Excessive intraoperative fluid (not blood) collections (or concern regarding this). Contaminated or dirty surgery

	
Positive air leak test (the intra-operative air leak test is a common intraoperative test used to identify mechanically insufficient anastomosis)
 
Poor vascularisation of the anastomosis (determined visually or by ICG fluorescence) (or concern regarding this).
 
Other reason identified (please specify)

Number of drains	Number
Type of drain(s) used	
Open (open drains drain fluid on to a gauze pad or into a stoma bag e.g. Penrose) / Close (tubes draining into a bag or bottle, e.g. Jackson-pratt).
 
Active (drains maintained under suction) / Passive (drains that have no suction and work according to the differential pressure between body cavities and the exterior).
 
(see REDCap for pictures)

Drain location	
Subcutaneous drain
 
Intraabdominal drain – pelvis
 
Intraabdominal drain – peritoneal cavity
 
Intraabdominal drain – posterior to the anastomosis
 
Intraabdominal drain – anterior to the anastomosis
 
Intraabdominal drain – near the anastomosis (not in contact)

Daily postoperative data points (to be completed for each inserted drain)	Required data (definition / comment)
Day of surgery is defined as Post-operative Day (POD) 0. The day after surgery is therefore defined as POD 1 and day 10 after surgery as POD 10.	
Volume drained (Daily POD 1-10)	
Millilitres (recordings of drain output must correspond to the entire day, i.e. 8am to 8am).
 
It is recommended that you collect data one day in retrospect.

Contents of drain output (Daily POD 1-10)	
Serous fluid (with or without blood staining) / Frank blood / Purulent / Faecal
 
(see REDCap for pictures)

Drain-related data points	Required data (definition / comment)

Day of drain removal	Post-operative Day (POD)
Surgical site infection	Yes – Site of Drain(s) / Yes – Other incision / No As defined by US Centers for Disease Control and Prevention (CDC)

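### The reason-for-drain field has no code for a drain left as routine surgeon or unit practice, so routine and undocumented drains cannot be reliably told apart at patient level

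*Protocol*

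**What the plan says.** Protocol section 7 (Outcome Measures) defines the primary outcome as adherence to ERAS guidance, expressed through the rate at which routine prophylactic drains are inserted. Section 3 (Study Aims) adds a secondary aim: "To explore the clinical decision-making process for drain placement after colorectal surgery". Section 16 (Patient and Public Involvement) says that the centre survey and the case report form will help to explore whether surgeons adhere and, "if not, understand their reasons for not being compliant".

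The patient-level field on motive is 'Reason for drain identified' in Appendix A. Its options, in order, are:
- the first two, which run together in the table: "Not identified Excessive intraoperative blood loss (or concern regarding this")
- the next two: "Excessive intraoperative fluid (not blood) collections (or concern regarding this). Contaminated or dirty surgery"
- a positive air leak test
- "Poor vascularisation of the anastomosis (determined visually or by ICG fluorescence) (or concern regarding this")
- "Other reason identified (please specify")

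A separate field records whether any abdominal drain was inserted, Yes or No. Section 2 (Summary) requires each centre to complete a survey on its local drain practices.

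**The concern.** The audited property is routineness. The guideline recommendation reproduced in section 13 is against routine use, not against every drain. To count routine drains patient by patient, the form must separate a drain left by habit or policy from one left for something found at that operation. All five substantive codes are of the second kind, and none is of the first.

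Take an uncomplicated anterior resection by a surgeon who always leaves a pelvic drain, where the operation note records the drain and nothing more. One collector will choose 'Not identified'. Another, who knows the surgeon's habit, may write 'routine' under 'Other'. A drain placed for a real but unwritten worry at another hospital also becomes 'Not identified'. The first and third records then look the same although only one departs from the guideline. The first and second look different although they are the same event.

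At stake are the numerator of the primary outcome, if it is to mean routine drains rather than all drains, and the breakdown of reasons for non-adherence that the form is meant to supply.

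**Working it through.** The protocol states no figure on this point, so there is nothing to reproduce. The check compares the option list with what it has to serve.

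**1. Options against the primary outcome.** Of the seven options, five are case-specific triggers (blood loss, other fluid, contamination, positive air leak test, poor perfusion), one is a null category and one is free text. Codes that mean routine practice or policy: none. The Yes/No insertion field gives total drain use, not routine use.

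**2. Options against the reasons the protocol gives.** Study Background says: "Reasons to justify drainage after colorectal surgery include: prevention of complicated intra-abdominal collections; early detection of haemorrhage, anastomotic leakage, or other complications", and goes on to fewer leaks and less pelvic sepsis. These are purposes, whereas the coded options are triggers. The rider about concern, attached to the blood-loss, fluid and vascularisation options, already covers part of the preventive and early-detection ground. The clear gap is the routine code, not the absence of purpose codes.

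**3. The same dictionary makes both missing distinctions elsewhere.** The method by which a collection was identified includes a code for imaging done routinely under hospital policy. The air leak field keeps a recorded negative apart from 'not recorded'. The drain-reason field has neither a policy code nor a separation of 'no specific reason' from 'not documented'.

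**4. What the other data recover.** Appendix A separately records perforation, urgency, contamination, air leak result, intraoperative transfusion and intraoperative complications. A 'Not identified' drain with a positive entry in one of these is plausibly indicated. One with none of them is plausibly routine, but may equally reflect an unwritten concern. The survey describes a centre's habits, not why a given patient was drained.

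**5. Size.** Let d be the share of patients drained and u the share of drained records coded 'Not identified'. The share of the cohort that the reason field alone leaves ambiguous is d × u. The document gives neither input. Its one related figure, 35%, is a share of centres that drain most of their patients, not a share of patients. The inputs below are therefore assumptions, applied to the anticipated 5,000 patients.

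| Assumed d | Assumed u | d × u | Patients of 5,000 |
|---|---|---|---|
| 0.35 | 0.20 | 0.07 | 350 |
| 0.30 | 0.40 | 0.12 | 600 |
| 0.35 | 0.60 | 0.21 | 1,050 |
| 0.40 | 0.60 | 0.24 | 1,200 |
| 0.50 | 0.80 | 0.40 | 2,000 |

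A spread from 7% to 40% shows that the result follows the assumptions. The operative fields in step 4 would shrink any of these figures, and so would more use of 'Other', through a lower u. The table shows how the effect scales and is not an estimate of it.

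**The case against.** The strongest reply is that the information is spread over several sources and the reason field need not carry it alone. The mandatory centre survey can capture unit routine; the 35% figure in Study Background came from such a survey. Free text can hold a routine or policy reason. The operative fields allow part of 'Not identified' to be classified. Treating a drain with no identified case-specific reason as routine is a defensible working definition, and an analysis plan not shown here may adopt it.

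Much of this stands. A reader might infer that the decision-making aim cannot be answered, that every routine drain is forced into 'Not identified', or that the true routine share of that category could be anything from none to all. The documents support none of these. The coded triggers, free text and survey all inform the aim. 'Other' is open to routine drains. The operative fields narrow the ambiguous group.

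The case for separate prevention and early-detection codes is also weak. Those purposes describe nearly every prophylactic drain and overlap with the options that already mention concern.

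What does not stand is the idea that the analysis can repair the gap. A rule that counts 'Not identified' as routine is only as good as the category, which by construction also holds undocumented reasons. Nothing in the dictionary tells collectors at about 300 anticipated centres when a habitual drain belongs under 'Not identified' and when under 'Other'. The survey's content is not shown. Sections 9 and 11 rule out centre-level analysis and hospital comparisons; pooled description of survey answers seems still allowed, but that does not give a patient-level reason.

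**Conclusion.** The point holds for the patient-level split between routine and indicated drains. The form has no code for routine practice and does not separate it from missing documentation, although the primary outcome is worded in terms of routine drains and a secondary aim concerns the decision to drain. The split can be made partly, from other fields and free text, but not reliably.

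The overall drain insertion rate is not affected. The decision-making aim is weakened, not defeated. The size cannot be determined from the protocol, because it depends on a drain rate and a documentation rate that the protocol does not give. The conclusion assumes that the live form carries the options printed in Appendix A, and that some operation notes record a drain without a reason.

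**What to change.** In the 'Reason for drain identified' field of Appendix A and in REDCap:
1. Add a coded option: 'Routine practice of surgeon or unit, no case-specific reason'.
2. Rename 'Not identified' to 'Reason not documented', so that it means only that.
3. Add one sentence telling collectors to check with the operating team when the note is silent, and to use 'Reason not documented' only if that gives no answer.

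The third step is feasible because collection is prospective, and section 8 already sends collectors to ward doctors and nurses for drain output. Separate prevention and early-detection codes are optional.

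The cost is one or two extra drop-down choices, a sentence of instruction and an occasional brief question to the team. No patient pathway changes.

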▲ If an in-hospital patient recovering from another primary procedure NOT previously included undergoes emergency surgery, this **MUST** be included in the study as emergency case. ▲

i.e. Patient A is recovering from an AAA repair and undergoes large bowel resection due to bowel ischaemia one day later the previous surgery. He was correctly not included after the AAA repair, as that is a primarily vascular procedure and it did not involve any large bowel resection, but should be included after the bowel resection.

- ▲ You should collect data on consecutive elective patients operated at your hospital during the data collection period. **All eligible patients** must be included. Strategies to identify consecutive patients could include: ▲
- Daily review of elective theatre lists.
 - Daily review of handover sheets and ward lists.
 - Daily review of theatre logbooks
 - Daily on call review of patients undergoing emergency surgery

7. Outcome Measures

I. Primary outcome measure:

- Adherence to selected Enhanced Recovery After Surgery (ERAS) guidelines regarding rate of routine prophylactic drain insertion in colorectal surgery (22).

II. Secondary outcome measures:

- Rate of intra-abdominal postoperative collections, defined as collections which alter the normal postoperative course (e.g. requiring either medical, radiological, endoscopic or surgical intervention) (23).
- Time-to-diagnosis (days) of intra-abdominal postoperative collections defined as collections which alter the normal postoperative course (e.g. requiring either medical, radiological, endoscopic or surgical intervention) (23).
- Rate of drain-related complications defined as:
 - Surgical site infection (Centers for Disease Control and Prevention – CDC – definition: A surgical site infection is an infection that occurs after surgery in the part of the body where the surgery took place);
 - Cutaneous irritation at the drain insertion site (defined as reversible damage of the skin associated with rash, dry skin, itchiness, red discolouration and/or hives);
 - Small bowel evisceration and herniation of omentum (defined as prolapse of small bowel and/or omentum through the drain site after the removal of the drain);
 - Bowel injury (defined as intraoperative identification of or CT-proven drain-related iatrogenic bowel perforation) (7,24).

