Appendix A: Data Dictionary

Please use the case report form together with this Data Dictionary to facilitate data collection

Preoperative data points	Required data (definition / comment)
Patient age	Years (whole years at the time of operation)
Patient gender	Male / Female
Patient ASA grade	Grade I-V (Full ASA classification available at: https://www.asahq.org/resources/clinical-information/asa-physical-status-classification-system).
Smoking status	Current (includes those who stopped smoking within 6 weeks), Previous , Never .
Patient height	Meters (record to two decimal places)
Patient weight	Kilograms (record to one decimal places)
Body Mass Index (if either weight or height unknown)	Underweight (<18.5), Normal range (18.5-24.9), Overweight (25-30), Obese (>30).
History of abdominal surgery	Yes / No
Pre-existing abdominal stoma	Yes – colostomy / Yes – jejunostomy or ileostomy / No stoma
History of ischaemic heart disease	Yes (Myocardial infarction or Angina) / No
History of congestive heart failure	Yes / No

History of cerebrovascular disease	Yes (transient ischemic attack or stroke) / No
History of diabetes mellitus	Yes (Type 1) / Yes (Type 2) / No
Control of diabetes mellitus	IF diabetes mellitus present Yes, insulin controlled / Yes, tablet controlled / Yes, diet controlled / No
Last pre-operative blood test values	Haemoglobin (grams / litre) / White Cell Count ($\times 10^9$ / litre) / estimated Glomerular Filtration Rate (ml / min) / C Reactive Protein (milligrams / litre).
History of immunosuppression	HIV (antiretroviral therapy, no/unknown), Steroids (yes: oral, intravenous or topical e.g. prednisolone, fludrocortisone, dexamethasone, no), Other immunosuppressive drug (yes, e.g. azathioprine, methotrexate, biologic agents, no), Chemotherapy (yes, current chemotherapy or if the last cycle was within 12 weeks of operation, no).
Operative data points	Required data (definition / comment)
Underlying pathology/indication	Malignancy / Inflammatory bowel disease / Diverticular disease / Bowel ischaemia / Small bowel obstruction / Large bowel obstruction / Other benign
Perforated bowel	Yes / No

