Surgical site infection type	Yes - Superficial (skin or subcutaneous tissue) / Yes - Deep (fascial and muscle layers) / Yes - Organ/Space SSI (intrabdominal) / No .
Small bowel evisceration/herniation of omentum	Yes – Site of Drain(s) / Yes – Other incision / No Prolapse of small bowel and/or omentum through an incision.
Drain-related iatrogenic bowel perforation	Yes - Intraoperative / Yes – Postoperative (not during removal) / Yes – Postoperative (during removal) / No.
Drain-related skin irritation	Yes (reversible damage of the skin at the drain insertion site associated with rash, dry skin, itchiness, red discolouration and/or hives) / No
Other Drain-related complication	Please specify
Reason(s) for drain removal	
1. Clinical rationale:
 
a). Drain output satisfactory (Yes, No) - if yes: low volume, (haemo)serous fluid, other (please specify).
 
b). Drain-related complications.
 
c). Inadvertent/premature drain withdrawal.
 
d). Other (please specify)
 
2. Radiological confirmation of no significant ongoing collection (Yes - pre removal, Yes - post removal, No).

Post-operative blood transfusion	Yes / No
Day of blood transfusion	Post-operative Day (POD)
History of collection(s) requiring treatment within 30 days (either medical, surgical, endoscopic, radiological)	Yes / No
Day of collection(s) identification	Post-operative Day (POD)

Collection(s) identification method	
1. Clinical only
 
a). Symptoms. b). Change in drain output (if inserted at time of surgery).
 
2. Radiological
 
a). Imaging due to clinical suspicion b). Routine imaging as per hospital policy c). Incidental finding (imaging for other indication).

Collection(s) treatment	
Conservative management (none or antibiotic therapy) Percutaneous drainage Surgery

Total postoperative antibiotic duration	
Number of days (Total antibiotic duration including both intravenous and oral antimicrobial therapy for the treatment of the collection(s). Post-operative antimicrobial therapy started before the identification of the collection(s) should not be included.)

Outcome data points	Required data (definition / comment)
Anastomotic leak within 30 days	Yes - Radiological diagnosis / Yes - Surgical diagnosis / No
Day of anastomotic leak diagnosis	Post-operative Day (POD)
Length of hospital stay (days)	Days
30 day readmission	Yes / No

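### The surgical site infection site field has no option for a non-incisional infection, so an isolated organ/space infection cannot be coded consistently, and the drain-related complication rate depends on which field is used

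*Protocol*

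**What the plan says.** Section 7 of the protocol lists a secondary outcome introduced as "Rate of drain-related complications defined as", and SSI is the first of its components. It gives the definition as: "A surgical site infection is an infection that occurs after surgery in the part of the body where the surgery took place". Nothing there limits the component to infection at the drain site.

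Appendix A, under the drain-related data points, records SSI in two adjacent rows:

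- The first row, which I call the site row, offers "Yes – Site of Drain(s) / Yes – Other incision / No As defined by US Centers for Disease Control and Prevention (CDC").
- The second row is the SSI type. It offers superficial, deep and, as its last two answers, "Yes - Organ/Space SSI (intrabdominal) / No".

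The appendix opens with the instruction "Please use the case report form together with this Data Dictionary to facilitate data collection". The case report form is not part of the document. Neither row says whether one answer or several may be given, and nothing says how the two rows relate to each other.

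**The concern.** The outcome definition and the type row treat an intra-abdominal infection as an SSI. The site row has nowhere to put one. Two careful collaborators could code the same pelvic abscess differently, and each could defend the entry.

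The site row is also the only place in the dictionary where an infected drain site is separated from an ordinary wound infection. If it takes one answer only, a patient infected at both places loses one of them at source.

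At stake is one component of a secondary outcome, in a study about drains and intra-abdominal collections. The primary outcome, adherence to the guideline on routine drain placement, is not affected. Section 14 sets an accuracy target above 98% for independently re-collected outcome fields. A field with no correct answer for a foreseeable case can create disagreements there that are not the centre's fault.

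**Working it through.** The protocol gives no SSI rates and no figure to reproduce, so the check is logical: take the possible infection patterns and try to complete both rows truthfully.

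**Case A: isolated organ/space infection.** The type row takes organ/space. In the site row, the drain-site and other-incision answers are untrue, and the negative answer contradicts both the type row and the section 7 definition. No pair of entries is both true and consistent. Allowing several ticks does not help, because the missing category is not on the list.

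**Case B: drain site and another incision both infected.** No combined answer is listed. If the row is single choice, one site is lost. If it is multiple choice, both are recorded, but depth in the type row is not tied to a site.

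**Case C: superficial drain-site infection plus organ/space infection.** The site row can be completed as drain site. If the type row is single choice, one of the two types is lost; if multiple choice, both are kept.

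The next step is to see how each case enters the section 7 component. The text leaves open which row defines it, so three readings are set out:

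| Case | Any SSI, from the site row | Any SSI, from the type row | Drain-site SSI only, from the site row |
|---|---|---|---|
| A | Not counted if coded negative; counted if placed at an incision | Counted | Counted only if wrongly placed at the drain site |
| B | Counted under either code | Counted | Single choice: counted or lost, depending on the code chosen. Multiple choice: counted |
| C | Counted | Counted | Counted |

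Case A changes across readings and, within a reading that uses the site row, with the collaborator's choice. Case B matters only if the drain-site infection rate is reported separately or used as the component, and only if the row is single choice.

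For Case B under single choice, the relative undercount of drain-site infections is

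P(another incision also infected, given drain-site SSI) × P(the other incision is the one coded).

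The protocol gives neither factor. The product is 0 if collaborators always code the drain site, and there is no loss at all if several answers may be ticked.

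**Is the row single choice?** The pattern of two qualified positive answers and one negative is also used for diabetes type, anastomosis creation and anastomotic leak diagnosis, which read as one answer per patient. Slashes alone prove nothing: the blood-test row separates values that are all collected in the same way ("Haemoglobin (grams / litre) / White Cell Count" and so on). Single choice is likely but not established.

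**The case against.** The strongest reply has four parts.

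1. A reader might infer that an organ/space infection cannot be recorded at all. That is wrong: the type row takes it. A collection needing treatment is also captured separately in Appendix A, with its day, method of identification and treatment. The gap is in the site row and in its agreement with the type row.

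2. A reader might infer that a patient infected at two sites can record only one. The document does not say so. The case report form and the REDCap screens are not shown, and several answers may be allowed there. This part is therefore conditional.

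3. A reader might infer that the two rows cannot be reconciled afterwards. Often they can: a negative site entry with organ/space as the type is recognisable as a non-incisional infection. The difficulty is the other coding. If the type row is single choice, an incision with organ/space as the type could be an isolated organ/space infection misplaced, or a true incisional infection with only the deeper type recorded. The data would not separate these.

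4. On the wording of section 7, a patient infected at both drain site and wound is SSI-positive under either code, so double infection does not change that rate. This is correct. The loss in Case B bears on a drain-site rate, which the site row is evidently built to provide but which section 7 does not define.

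A figure is also tempting. Assuming co-infection in 25% to 50% of drain-site infections, with half to all coded to the other incision, gives 0.25 × 0.5 = 12.5% to 0.5 × 1 = 50%. Nothing in the protocol supports these inputs, and the range leaves out zero, which is possible. It should not be used.

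None of the four parts removes Case A, which holds however the form is built.

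**Conclusion.** The concern holds in a limited form. The site row has no answer for a non-incisional infection, while the type row and section 7 both treat such an infection as an SSI. An isolated organ/space infection cannot be entered truthfully and consistently in both rows, and whether it counts in the drain-related complication rate depends on a choice that the protocol does not make. This conclusion needs no assumption about how the form is built.

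The loss of drain-site infections when another incision is also infected is conditional on single choice. Its size cannot be derived from the protocol and may be zero.

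The change should be made: the outcome is secondary, but a site misrecorded at source cannot always be recovered in analysis, and the correction is small.

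**What to change.** Replace the two rows with three separate Yes/No items for each patient:

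- drain-site infection (patients with a drain), with superficial or deep if present;
- infection at another incision, with superficial or deep if present;
- organ/space infection.

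This works whether the present rows are single or multiple choice, and it ties depth to site.

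Then state in section 7 which item or items form the SSI component of the drain-related complication rate. The current text does not restrict SSI to the drain site, so limiting the component to the first item would redefine the outcome and should be written down as a deliberate decision.

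If the form cannot be rebuilt, the minimum is to add a non-incisional answer to the site row, state that more than one answer may be ticked in each row, and name the row that governs the outcome. That resolves Case A but still leaves depth unlinked to site.

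The cost is an edit to the form and the data dictionary, and slightly more data entry.
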